### Cleveland Clinic Score:(Lauer et al., 2007)

Arbitrarily, we assume CCS will predict significant CAD with high probability if the value is  $> 140$  and low probability if the value is  $< 100$ .

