## Statistical Methods

Using angiographic evidence of CAD as the reference, area under the curve (AUC) of receiver operator characteristic (ROC) plots will be determined for the ST response alone and for each treadmill score. The AUC for each treadmill score will be compared with the AUC of the ST response alone and the AUCs of the other treadmill scores. A significant difference is defined as a z-score  $>1.96$ , with  $z\text{-score} = (AUC_1 - AUC_2) / (\text{SE}_1^2 + \text{SE}_2^2)^{1/2}$ . The predictive accuracies of the DTS, the Simple Treadmill Score and Cleveland Clinic Score to stratify patients into high or low likelihood for CAD will be calculated and compared. Test of agreement will be calculated using Kappa statistics. Statistically significant difference between predictive accuracies is defined as a p value  $<0.05$  using the two-tailed Fischer's exact test. Statistical analysis will be performed with the SPSS.

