### Chi-Square Tests

	Value	Df	Asymp. Sig. (2-sided)	Sig. ExactSig. (2-sided)	Exact Sig. (1-sided)
Pearson Chi-Square					
Continuity Correction b					
Likelihood Ratio					
Fisher's Exact Test					
Linear-by-Linear Association					
N of Valid Cases					

a. 1 cells (25.0%) have expected count less than 5. The minimum expected count is 2.74.

b. Computed only for a 2x2 table

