### Chi-Square Tests

	Value	Df	Asymp. Sig. (2-sided)	Exact Sig. (2-sided)	Exact Sig. (1-sided)
Pearson Chi-Square Continuity Correction b Likelihood Ratio Fisher's Exact Test Linear-by-Linear Association N of Valid Cases					

a. 1 cells (25.0%) have expected count less than 5. The minimum expected count is 3.06.

b. Computed only for a 2x2 table

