### Chi-Square Tests

	Value	df	Asymp. Sig. (2-sided)	Exact Sig. (2-sided)	Exact Sig. (1-sided)
Pearson Chi-Square					
Continuity Correction b					
Likelihood Ratio					
Fisher's Exact Test					
Linear-by-Linear Association					
N of Valid Cases					

a. 1 cells (25.0%) have expected count less than 5. The minimum expected count is 3.54.

b. Computed only for a 2x2 table

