## Appendix A

### Treadmill Scores and their calculation

The DTS will be calculated as  $DTS = \text{exercise time} - (5 \times \text{ST deviation}) - (4 \times \text{exercise angina})$ , with 0 = none, 1 = non-limiting, and 2 = exercise-limiting angina. The METs will be calculated by modified Bruce protocol and be inputted into the DTS equation (Fletcher et al., 1995). Based on the study by Shaw *et al.* (1998), a  $DTS < +5$  is considered abnormal. High risk when  $DTS < -10$  and low risk when  $DTS > +5$ .

The simple Treadmill Score for men will calculated as follows:

$(6 \times \text{maximal heart rate code}) + (5 \times \text{ST-segment depression code}) + (4 \times \text{age code}) + \text{angina pectoris code} + \text{hypercholesterolemia code} + \text{diabetes code} + \text{treadmill angina index code}$ .

The simplified score had a range from 6 to 95, with  $< 40$  designated as low probability, between 40 and 60 was intermediate probability, and  $> 60$  was high probability for CAD.

For male patient

Variable	Choose Response	Sum
Maximal HR	$<100 \text{ bpm} = 30$	
	$100-129 \text{ bpm} = 24$	
	$130-159 \text{ bpm} = 18$	
	$160-189 \text{ bpm} = 12$	
	$190-220 \text{ bpm} = 6$	
Exercise ST depression	$1 - 2 \text{ mm} = 15$	
	$>2 \text{ mm} = 25$	
Age	$>55 \text{ yr} = 20$	
	$40-55 \text{ yr} = 12$	
Angina history	Definite/typical = 5	
	Probable/atypical = 3	

[figure not shown]
	Non-cardiac pain = 1	
Hypercholesterolemia	Yes = 5	
Diabetes	Yes = 5	
Exercise test: induced angina	Occurred = 3	
	Reason for stopping = 5	
	Total score:	

For Female patients

Variable	Choose Response	Sum
Maximal HR	<100 bpm = 20	
	100-129 bpm = 16	
	130-159 bpm = 12	
	160-189 bpm = 8	
	190-220 bpm = 4	
Exercise ST depression	1 – 2 mm = 6	
	>2 mm = 10	
Age	>65yr = 25	
	50-65 yr = 15	
Angina History	Definite/typical = 10	
	Probable/atypical = 6	
	Non-cardiac pain = 2	
Smoking	Yes = 10	
Diabetes	Yes = 10	
Exercise test: Induced angina	Occurred = 9	
	Reason for stopping = 15	
Estrogen status	+ve = -5, -Ve = 5	
	Total =	

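### The accuracy comparison of CCS with DTS and STS rests on CCS cut-offs the plan calls arbitrary, so score-versus-score claims should rest on the planned AUC comparison

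*Combined protocol and SAP*

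**What the plan says.** **CCS classes.** Appendix A, under Cleveland Clinic Score, states: "Arbitrarily, we assume CCS will predict significant CAD with high probability if the value is" above 140; below 100 is low. Nothing is said about values from 100 to 140. The Rationale adds that, to the authors' knowledge, CCS has not been tested as a diagnostic predictor of CAD.

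**DTS classes.** Appendix A cites a 1998 study. A score below +5 "is considered abnormal. High risk when" it is below -10, and low risk when it is above +5.

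**STS classes.** Below 40 is "designated as low probability, between 40 and 60 was intermediate probability, and" above 60 is high. These limits follow the men's formula. The women's table has different points and no limits.

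**Use of the classes.** Statistical Methods provides for "The predictive accuracies of the DTS, the Simple Treadmill Score and Cleveland Clinic Score to stratify patients into high or low likelihood for CAD" to be calculated and compared, with a two-tailed Fisher's exact test at p < 0.05, and for kappa. The crosstabs in Dummy Tables/Graphs and items 26 to 28 of the data collection form have only a low and a high class.

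**Cut-off-free analysis.** Statistical Methods also plans ROC AUCs for the ST response and each score, each score being compared with the ST response and with the other scores.

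**Dummy-table footnotes.** The table bodies are empty, but the notes carry specific values: "The minimum expected count is 2.74" (DTS), "The minimum expected count is 3.06" (STS) and "The minimum expected count is 3.54" (CCS). The AUC table notes ties between the CAD groups for all three scores.

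**The concern.** Specific Objective 2 is to compare the accuracy of the three scores. Accuracy describes a score together with a cut-off. A low or high accuracy for CCS at 100/140 may therefore say little about how well CCS discriminates. Followed as written, the plan could declare CCS better or worse than DTS or STS at p < 0.05 when the difference comes only from where the line was drawn. Readers would probably take that as a finding about the scores, and the stated purpose is to decide which patients can be spared angiography.

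The footnotes raise a second question. A minimum expected count cannot be computed from an empty table, so some data lie behind these notes. The plan does not say which data, or whether 100/140 was fixed before they were seen.

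**Working it through.** **1. The plan's own figure.** The only design calculation is a one-sample comparison of accuracy, 0.71 against 0.55:

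[1.28 × √(0.55 × 0.45) + 1.96 × √(0.71 × 0.29)]² / 0.16² = (0.637 + 0.889)² / 0.0256 = 90.98, so 91. Allowing for 10% non-response, 91 / 0.9 = 101.1, so 102.

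Both figures reproduce. The calculation is built on accuracy, but it involves neither CCS nor its cut-off. Its 16 points are a DTS-against-fixed-value contrast, not a margin between scores.

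**2. How far the cut-off alone moves accuracy.** Assumptions: equal-variance binormal score; AUC 0.80; CAD prevalence 50%, 60% or 72% (72% is the figure for men in a cohort cited in the Literature Review; the others are assumed).

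- Separation d = √2 × Φ⁻¹(0.80) = 1.190.
- At cut-off c, in SDs from the non-CAD mean: specificity = Φ(c), sensitivity = 1 − Φ(c − d).
- Accuracy = prevalence × sensitivity + (1 − prevalence) × specificity.

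| c | Sensitivity | Specificity | Accuracy, 50% | Accuracy, 60% | Accuracy, 72% |
|---|---|---|---|---|---|
| 0 | 0.883 | 0.500 | 0.691 | 0.730 | 0.776 |
| 0.3 | 0.813 | 0.618 | 0.716 | 0.735 | 0.759 |
| 0.6 | 0.723 | 0.726 | 0.724 | 0.724 | 0.723 |
| 0.9 | 0.614 | 0.816 | 0.715 | 0.695 | 0.671 |
| 1.2 | 0.496 | 0.885 | 0.691 | 0.652 | 0.605 |

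For c from 0 to 1.2 the spread is 3 points at 50% (0.691 to 0.724), 8 at 60% (0.652 to 0.735) and 17 at 72% (0.605 to 0.776). For c from −1 to +2 it is 15, 22 and 35 points (0.57 to 0.72, 0.52 to 0.74 and 0.42 to 0.78). The lowest of these, 0.42, needs a cut-off with only 21% sensitivity.

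**3. The middle band.** Same score, 65% prevalence (assumed), and an unassigned band of ±0.5 SD around the midpoint of the two distributions:

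- band dropped: accuracy 0.797, with 67% of patients classified;
- band counted as low: 0.652;
- band counted as high: 0.749.

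The handling of the band therefore moves accuracy by up to 14 or 15 points (0.797 − 0.652). The plan has no rule for CCS 100 to 140, for STS 40 to 60, or for DTS −10 to +5 if the high-risk rule defines a positive. If below +5 defines a positive, only a DTS of exactly +5 is unplaced.

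**4. The footnotes.** In a 2×2 table the minimum expected count is r × m / N, where r is the smaller score class, m the smaller CAD group and N the table total. I required one N (10 to 102) and one m for all three tables, with exactly one expected count below 5 in each. The only solution is N = 87, m = 14, r = 17, 19 and 22:

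17 × 14 / 87 = 2.74; 19 × 14 / 87 = 3.06; 22 × 14 / 87 = 3.54.

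About 8% of random triples between 2.50 and 3.99 would also have a common solution. If N differs between tables, many combinations fit.

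**The case against.** Four points can be made for the plan.

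- **AUC is already there.** The plan includes pairwise AUC comparisons, which need no threshold. A reader might infer that the whole ranking of scores is an artefact of the cut-off. The documents do not support that: only the accuracy, Fisher and kappa results are exposed. This objection stands and limits the point.
- **An arbitrary cut-off is not in itself an error.** The authors knew of no diagnostic use of CCS, so they had no threshold to cite, and they say openly that they assumed one. A cut-off fixed in advance may perform poorly but is not optimistic. This stands, but it does not make accuracy at that cut-off a fair comparison between scores.
- **The effect can be small.** With moderate cut-offs and prevalence near 50% it is about 3 points. This also stands. The prevalence of CAD in this angiography sample is unknown, and the effect grows as prevalence moves away from one half.
- **The footnotes prove little.** A reader might infer that 100/140 was tuned on outcome data. The documents do not support that. The notes could come from a pilot, a template or other earlier output. The N = 87 solution needs one common N. If that N is right, every patient was placed in one of two classes, so those tables did not leave out the middle band. They say nothing direct about how 100/140 was chosen. The hypertension definition cites a November 2017 guideline, and November 2017 is the last month of the stated study period. That makes the question reasonable but does not answer it.

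A reader might also contrast an arbitrary CCS with comparators at clean published cut-offs. That contrast fails: DTS has two candidate rules for a positive, and the women's STS has no stated limits.

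**Conclusion.** The concern holds in a limited form. The accuracy, Fisher and kappa comparisons involving CCS depend on a threshold that the plan itself calls arbitrary, so a difference from DTS or STS can arise with no difference in discrimination. The size is about 3, 8 and 17 accuracy points at 50%, 60% and 72% prevalence for moderate cut-offs, and more at extreme ones. This rests on an assumed equal-variance binormal score with AUC 0.80. The documents give no distribution for CCS, so where 100 and 140 fall on this scale is unknown.

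The weakness is not confined to CCS, because incomplete class rules affect all three scores. The AUC comparison is free of the problem. Whether the cut-offs came before any outcome data is an open question of provenance, not a finding.

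**What to change.** 1. In Statistical Methods, make the planned AUC comparison the sole basis for any claim that one score is better than another.
2. Where the text has the accuracies "to stratify patients into high or low likelihood for CAD will be calculated and compared", label CCS accuracy at 100/140 exploratory and report it over a range of cut-offs. Reporting it at a sensitivity matched to the other scores is an alternative, though imprecise if one CAD group is small.
3. In Appendix A, state one two-class rule for each score and sex, with its source. It should say which DTS limit defines a positive, give limits for the women's STS, and say where the middle band goes. Apply the same rules in the crosstabs and the data collection form.
4. Ask the sponsor which data produced the minimum expected counts and the tie note in the dummy tables, and whether 100/140 was fixed before those data were seen. Record the answer in the plan.

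The cost is wording and some re-analysis, with no new patients. The downside is that 100/140 cannot be presented as a validated diagnostic cut-off.

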**Fig: Cleveland Clinic Score Nomogram.**

## Appendix B

### Study design flow chart:

**Patient with Stable chest pain who underwent ETT and admitted for CAG**

**Patient selected according to Inclusion and exclusion criteria**

**DTS, Simple Treadmill Score, Cleveland Clinic score calculated**

**Report collection after CAG**

**Data for analysis**

## Appendix C

### Questionnaire/ Data Collection Form

**Title: A comparative study of different treadmill scores to diagnose Coronary Artery Disease in among patients attending Bangabandhu Sheikh Mujib Medical University.**

**SL No.....**

**Date: .....**

**Name: .....**

**Address: .....**

**Hospital Reg. No. .....**

**Date of ETT: ..... Date of CAG: ..... CD No.....**

#### **Demographic and anthropometric variables:**

- |                    |                   |                      |
|--------------------|-------------------|----------------------|
| 1. Age:            | .....Yrs          |  |
| 2. Gender:         | 1= Male 2= Female |  |
| 3. Weight:         | ..... Kg          |  |
| 4. Height:         | ..... cms         |  |
| 5. Marital status: | 0= No 1= yes      |  |

#### **Baseline variables:**

- |                            |                                      |                      |                      |
|----------------------------|--------------------------------------|----------------------|----------------------|
| 6. Anginal pain:           | 0= Non cardiac 1=Typical 2= Atypical |  |                      |
| 7. Past Smoker:            | 0= No                                | 1= Yes               |  |
| 8. Current smoker:         | 0= No                                | 1= Yes               |  |
| 9. Hypertension:           | 0= No                                | 1= Yes               |  |
| 10. NIDDM:                 | 0= No                                | 1= Yes               |  |
| 11. IDDM:                  | 0= No                                | 1= Yes               |  |
| 12. Oestrogen status:      | 0= Negative                          | 1= Positive          |  |
| 13. Family history of CAD: | 0= No                                | 1= Yes               |  |

14. Sudden death of 1st degree relatives: 0= No 1= Yes

### Biochemical Investigations:

15. Lipid profile: TC..... mg/dl; LDL..... mg/dl; HDL..... mg/dl; TG..... mg/dl

16. RBS: .....mg/dl

17. Serum creatinine: .....mg/dl

### Exercise test variables:

18. Duration of exercise: .....min

19. METs .....

20. Maximum Heart Rate: .....bpm

21. Peak Systolic BP: .....mmHg

22. Maximum ST segment depression: .....mm

23. Exercise induced angina: 0= No angina 1= Non-test limiting

2= Test limiting angina

24. Abnormal heart rate recovery: 0= No 1= Yes

25. Frequent VE during recovery: 0= No 1= Yes

26. Duke Treadmill Score: ..... 0= Low risk

1= High risk

27. Simple Treadmill Score: ..... 0=Low probability

1=High probability

28. Cleveland Clinic Score: ..... 0=Low probability

1= High probability

### Coronary angiogram:

29. Extent of disease: 0= Normal, 1=SVD, 2=DVD, 3=TVD, 4=LM

## Appendix E

### Abbreviations

ACC.....	American College of Cardiology
AHA.....	American Heart Association
BMI.....	Body Mass Index
BP.....	Blood Pressure
BSMMU.....	Bangabandhu Sheikh Mujib Medical University
CAD.....	Coronary Artery Disease
DVD .....	Double Vessel Disease
DTS.....	Duke Treadmill Test
CAG.....	Coronary angiogram
ETT.....	Exercise Tolerance Test/ Exercise Treadmill Test
ECG.....	Electrocardiogram
HDL.....	High Density Lipoprotein
HR.....	Heart Rate
IDDM.....	Insulin dependent diabetes mellitus
IHD.....	Ischemic Heart Disease
HTN.....	Hypertension
LBBB.....	Left Bundle Branch Block
LVH.....	Left Ventricular Hypertrophy
LDL.....	Low density lipoprotein
MET.....	Metabolic Equivalent
MI.....	Myocardial Infarction
NIDDM.....	Non insulin dependent diabetes mellitus
SD.....	Standard Deviation
SPSS.....	Statistical Program for Social Science
SVD.....	Single Vessel Disease
TVD.....	Triple Vessel Disease
VE.....	Ventricular Ectopic
WPW.....	Wolf-Perkison-White syndrome
